7.2 Study Timeline

After receiving Center for the Clinical Trials Network (CCTN) approval of the final protocol, approximately 9-12 months of trial preparation activities will elapse prior to commencing enrollment (“go-live”) at Site 1. The intervention at Site 2 is anticipated to begin 6-9 months after go-live date at Site 1, and the intervention at Site 3 will begin 12-15 months after the go-live date at Site 1. Selection of Geisinger as Site 2 and Essentia as Site 3 occurred subsequent to the initial CCTN approval of the final protocol and initial IRB submission. Trial preparation will include obtaining Institutional Review Board (IRB) approval, customizing the OUD-CDS for each healthcare system, harmonizing data elements for EHR installation at each site, installing of EHR custom code at each site, recruiting and randomizing primary care clinics at each site, conducting PCP training at each site, integration of CDS into workflow at each site, and completing baseline PCP surveys at each site.

As noted previously, the COVID-19 pandemic delayed implementation by approximately 8 months. Accrual periods will range from 7 to 18 months based on site. During the accrual period, the study team will monitor accrual rates to determine when a sufficient number of patients have been enrolled to support the analysis plan. If enrollment is lower than expected, we may choose to extend the accrual period up to 3 additional months (through January 2023). Observation will begin with index dates at each site and are anticipated to continue through October 2023.

Anticipated Accrual + Observation Periods per Site:

- HealthPartners – April 2021 to Oct 2023 (31 months)
- Geisinger – Dec 2021 to Oct 2023 (22 months)
- Essentia – April 2022 to Oct 2023 (18 months)

Anticipated Accrual* Periods per Site:

- HealthPartners – April 2021 to Oct 2022 (18 months)
- Geisinger – Dec 2021 to Oct 2022 (10 months)
- Essentia – April 2022 to Oct 2022 (7 months)

* We may extend the accrual period an additional 3 months based on enrollment trends.

COMPUTE 2.0 Study Timeline

Study Timeline	Year 1		Year 2				Year 3				Year 4				Year 5		
	2019		2020		2021		2022		2023		2024						
	Quarter	3	4	1	2	3	4	1	2	3	4	1	2	3	4	1	2
Phase 1: Development Phase																	
Finalize protocol, obtain IRB approval (Site 1)																	
Obtain IRB approval at Sites 2 & 3																	
Customize OUD-CDS for each partner site																	

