13.1.2 Primary and Secondary Outcomes (Endpoints)

Primary outcome measures will include:

1. OUD diagnosis (in the problem list or as an ICD-10 visit code) within 30 days of index visit for patients identified by the OUD-CDS as being at high risk of OU
2. Naloxone prescription within 30 days of index visit for patients with OUD or identified by the OUD-CDS as being at high risk for OUD
3. MOUD orders or referral to OUD treatment within 30 days of index visit for patients with OUD or identified by the OUD-CDS as being at high risk for OUD
4. Total days covered by an MOUD prescription in the 90 days after index visit for patients with OUD or identified by the OUD-CDS as being at high risk for OUD

Secondary outcome measures will include:

1. OUD diagnosis (in the problem list or as an ICD-10 visit code) at index or within 90 days of index visit for patients identified by the OUD-CDS as being at high risk of OUD
2. Naloxone prescription at index or within 90 days of index visit for patients with OUD or identified by the OUD-CDS as being at high risk for OUD
3. MOUD orders or referral to OUD treatment at index or within 90 days of index visit for patients with OUD or identified by the OUD-CDS as being at high risk for OUD
4. Number of ED visits during the observation period for patients with OUD or identified by the OUD-CDS as being at high risk for OUD
5. Number of hospitalizations during the observation period for patients with OUD or identified by the OUD-CDS as being at high risk for OUD
6. Healthcare costs during the observation period for patients with OUD or identified by the OUD-CDS as being at high risk for OUD, compared with healthcare costs over the same interval preceding the observation period
7. Cost of OUD-CDS implementation and maintenance
8. All-cause mortality rates during the observation period for patients at high risk of OUD
9. Fatal and non-fatal opioid overdoses during the observation period for patients at high risk of OUD
10. Rates of OUD-CDS use in intervention clinics
11. PCP ratings of confidence in treating patients with OUD prior to go-live date and 9-months following go-live date
12. Intervention clinic PCP ratings of satisfaction and acceptability of the OUD-CDS at 9 months following go-live date

Exploratory outcome measures may include:

1. Number of non-waivered PCPs becoming buprenorphine waived during the intervention period, assessed via health system administrative data

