13.2.2.1 Statistical Power

A preliminary power analysis was conducted to estimate the minimum detectable difference in the likelihood of OUD diagnosis (H1.1), naloxone rescue kit order (H1.2) and MOUD order or referral for treatment (H2.2) within 30 days of the index visit, and the number of days covered by a MOUD prescription in the 90 days post-index (H2.2) among patients cared for in OUD-CDS relative to UC clinics (see **Section 13.4**). The power analysis relied on conservative assumptions regarding the numbers of randomized clinics (10, 30, 50) and of eligible patients (50 or 100 per clinic); a range of clinic intraclass correlations consistent with those observed for other process measures at HealthPartners (i.e., $ICC_{clin} = 0.01, 0.03, 0.05$); and central tendency estimates for the outcomes (2%, 5%, 10% and 20% or 70, 50, 30 days not covered in UC). Power estimates will be updated after Sites 2 and 3 are selected and preliminary data to inform analysis assumptions become available.

Effect size estimates for the binary outcomes were calculated using the NIH group randomized trial sample size calculator.[48] The difference in days covered was estimated using the Poisson regression module of PASS 11 software[49] after calculating an effective sample size (i.e., $N_{eff} = (n \text{ clinics} * m \text{ patients per clinic}) / (1 + (m-1) * ICC_{clin})$). In addition, the Poisson model power analysis was conducted to estimate the minimally detectable decrease in days NOT covered in the 90 days to post-index among OUD-CDS relative to UC patients to ensure that the estimated days in both groups remained between 0 and 90 days.

Table 3 summarizes the minimum detectable increases in outcome rates among OUD-CDS relative to UC patients given the aforementioned assumptions. Assuming 30 randomized clinics with 50 high risk patients each, that 5% of UC patients have an OUD diagnosis within 30 days of their index visit and $ICC_{clin} = 0.03$, the H1.1 analysis would be powered (power=0.80, $\alpha_2 = 0.05$) to detect a difference if $\geq 11.35\%$ (odds ratio = 2.43) of OUD-CDS patients have an OUD diagnosis within 30 days of their index visit. For an event occurring among 10% of UC patients given the

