Table 4 provides a comparable summary for the H2.2 outcome, days covered by a MOUD prescription in the 90 days post-index. The inverse of the H2.2 outcome was used to calculate the minimum detectable difference in MOUD coverage days to ensure that estimated decreases in days not covered (or, increases in days covered) remained between 0 and 90 days. Continuing with the assumptions from the prior examples, the H2.2 analysis would be sufficiently powered to detect a decrease in days not covered by a MOUD if UC patients had 50 of their 90 post-index days uncovered (40 covered) but OUD-CDS patients had at least 37.0 uncovered (53.0 covered) days.

Table 4. Minimum detectable decrease in 90 days post-index without a MOUD prescription among OUD-CDS relative to UC patients, assuming n=(50, 100) patients per clinic, m=(10, 30, 50) randomized clinics, ICC_{clin}=(.01, .03, .05) and 30, 50, 70 days not covered in UC.								
UC	RR	30	50	70	RR	30	50	70
	n patients / clinic = 50				n patients / clinic = 100			
ICC_{clin}	m=10 clinics (minimum site-specific)				m=10 clinics (minimum site-specific)			
0.05	0.615	18.5	30.8	43.1	0.638	19.1	31.9	44.7
0.03	0.665	19.9	33.4	46.5	0.695	20.9	34.8	48.6
0.01	0.731	21.9	36.4	51.2	0.775	23.2	38.7	54.2
ICC_{clin}	m=30 clinics (minimum study-wide)				m=30 clinics (minimum study-wide)			
0.05	0.760	22.8	38.0	53.2	0.775	23.3	38.8	54.3
0.03	0.739	22.2	37.0	51.7	0.813	24.4	40.6	56.9
0.01	0.836	25.1	41.8	58.5	0.864	25.9	43.2	60.5
ICC_{clin}	m=50 clinics				m=50 clinics			
0.05	0.809	24.3	40.5	56.6	0.822	24.7	41.1	57.5

0.03	0.836	25.1	41.8	58.6	0.852	25.6	42.6	59.7
0.01	0.871	26.1	43.6	61.0	0.893	26.8	44.7	62.5

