13.4 Significance Testing

The H1.1, H1.2 and H2.1 outcomes will be assessed 3 times for each patient – at the index visit (0 days), and 30 (for primary outcomes) and 90 days post-index. Outcomes that occur at an index visit will be coded as also having occurred by days 30 and 90. Similarly, outcomes that occur between days 1 and 30 will be coded as having occurred by days 30 and 90; and those occurring

between days 31 and 90 will be coded as having occurred by day 90. We expect that the documented actions that providers take will be overwhelmingly attributable to the index visit. Some actions that providers initiate at the index visit, such as placing a treatment referral order, may not be complete until considerations related to safety or availability are addressed. The primary outcome for H1.1, H1.2 and H2.1 will be assessed at 30 days so that these actions, likely initiated at the index visit, may be completed prior to assessing the outcome. It is possible that outcomes will not be documented for patients who have post-index visits within 90 days at non-participating clinics. We assume that these eventualities will be rare and equally likely across treatment groups.

Because virtually all of the information pertinent to the H1.1, H1.2 and H2.1 outcomes will be captured by the day 30 measure, the primary hypothesis test for these models will compare the likelihood of the day 30 outcome by treatment group. The primary hypothesis test for the H2.2 outcome will compare the likelihood of the day 90 outcome by treatment group. These comparisons will be evaluated using a two-sided test with a Type I error rate of 5%. Comparisons at other time points will aid understanding of how relative differences in OUD-CDS versus UC settings may increase or decrease in the short term. For example, OUD-CDS might initiate a course of provider actions that otherwise would not occur (increase) or merely hasten action that eventually takes place in UC settings (decrease).

The Aim 3 outcomes represent counts of events that accrue over the post-index observation periods. The event rates in OUD-CDS versus UC clinics will be evaluated using a two-sided test with a Type I error rate of 5%.

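### Table 4's worked cell for primary outcome H2.2 prints a rate ratio of 0.739 where the table's own method gives 0.793, so the stated detectable difference of 13.0 days should be 10.3; the variance behind the table is not stated

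*Combined protocol and SAP*

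**What the plan says.** Section 13.1.2 lists H2.2 as the fourth primary outcome: "Total days covered by an MOUD prescription in the 90 days after index visit for patients with OUD" or at high risk of it. Section 13.2.2.1 describes how its power was assessed: "The difference in days covered was estimated using the Poisson regression module of PASS 11 software", after total patients were reduced to an effective sample size by the usual design effect. The calculation was done on days not covered, "to ensure that the estimated days in both groups remained between 0 and 90 days".

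Table 4 gives one rate ratio (RR) for each combination of clinics, patients per clinic and ICC, and applies it to usual-care (UC) means of 30, 50 and 70 uncovered days. For 30 clinics of 50 patients with ICC 0.03 it prints RR 0.739 and 22.2, 37.0 and 51.7 days. The accompanying sentence uses the middle value: "UC patients had 50 of their 90 post-index days uncovered (40 covered) but OUD-CDS patients had at least 37.0 uncovered (53.0 covered) days".

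No standard deviation, dispersion parameter or baseline rate for uncovered days is given.

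**The concern.** In the 30 × 50 block of Table 4 the RRs read 0.760, 0.739 and 0.836 as the ICC falls from 0.05 to 0.03 to 0.01. A lower ICC gives a larger effective sample size, so the detectable RR should move steadily towards 1. The middle value moves the wrong way, and it is the one used for the worked example. That sentence is the only worked power statement for H2.2.

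The sentence also says *at least* 37.0 uncovered days. For a minimum detectable decrease, the intervention mean must be *at most* the stated value.

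A second question is which variance the table assumes. A Poisson model takes its variance from the mean, but one RR serves three very different means. Without the assumption, a reader cannot tell which columns are conservative.

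**Working it through.** **Inputs.** From Section 13.2.2.1: 30 clinics, 50 patients per clinic, ICC 0.03; power 0.80 and two-sided α 0.05, stated for the H1.1 example and carried over to H2.2. Section 13.4 also sets a two-sided 5% test. Section 2.2 gives 1:1 allocation.

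**Effective sample size** (the protocol's formula): N_eff = (30 × 50) / (1 + 49 × 0.03) = 1500 / 2.47 = 607.3.

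**Detectable RR** (standard Poisson-regression power formula, binary covariate split 50:50, baseline mean λ): solve

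ln(RR)² = [1.96 × 2 + 0.8416 × √(2 + 2/RR)]² / (N_eff × λ).

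The protocol does not give λ. With λ = 1, 17 of the 18 printed RRs reproduce to three decimals. The 30 × 50 block is:

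| ICC | N_eff | Computed RR | Printed RR |
|---|---|---|---|
| 0.05 | 434.8 | 0.760 | 0.760 |
| 0.03 | 607.3 | 0.793 | **0.739** |
| 0.01 | 1006.7 | 0.836 | 0.836 |

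**The ordering is wrong whatever the variance.** Three cells with a smaller N_eff than 607.3 print an RR closer to 1: 0.760 (434.8), 0.775 (502.5; 10 × 100, ICC 0.01) and 0.775 (504.2; 30 × 100, ICC 0.05).

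**What 0.739 would need.** At 80% power it requires N_eff = 360.9, so ICC = (1500/360.9 − 1)/49 = 0.064, outside the table's 0.01–0.05. At N_eff = 607.3 its power is Φ[(|ln 0.739| × √607.3 − 3.92) / √(2 + 2/0.739)] = 0.948.

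Other variants for this cell also miss it: one-sided 0.814, unpooled variance 0.785, α 0.0125 0.759, 40:60 allocation 0.789, 90% power 0.763. Only about 95% power (0.738) comes close, and that contradicts the stated 0.80.

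**Carry-through.** 0.739 × 30, 50 and 70 gives 22.2, 37.0 and 51.7 after rounding, so the day columns and the sentence were built on the wrong RR. With 0.7932 the values are 23.8, 39.7 and 55.5. At UC 50 the difference is 50 − 39.7 = 10.3 days, against 50 − 37.0 = 13.0.

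**Implied variance.** λ = 1 with one RR applied to every mean is equivalent to a UC patient-level SD equal to the UC mean. Setting λ to 30, 50 or 70 reproduces no cell: the smallest computed RR anywhere is 0.918, above the largest printed value of 0.893. On a 0–90 scale the largest possible SD at mean u is √[u(90 − u)], which is 42.4, 44.7 and 37.4 at 30, 50 and 70. A UC SD of 30 is therefore feasible at UC 30, but 50 and 70 are not feasible at UC 50 and UC 70.

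**Effect of the variance on the corrected cell.** Taking the largest possible variance in both arms, solve u₀ − u₁ = (1.96 + 0.8416) × √{[u₀(90 − u₀) + u₁(90 − u₁)] / (607.3/2)} for u₁:

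| UC mean u₀ | Maximum-variance u₁ | Corrected Table 4 value |
|---|---|---|
| 30 | 20.8 | 23.8 |
| 50 | 39.8 | 39.7 |
| 70 | 60.9 | 55.5 |

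**The case against.** The strongest reply is that little depends on this cell. Section 13.2.2.1 calls the analysis preliminary and presents a grid; the other 17 RRs are right, including 0.813 for 100 patients per clinic. Fifty patients per clinic is the minimum, and Section 13.2.2 considers far larger numbers plausible. The slip is conservative, and no clinic number or test depends on it. All of that stands. It limits the consequence but does not make the printed figure right.

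On the variance, the baseline mean of 1 is inferred, and describing it as SD equal to the mean is exact only for the UC arm. In the intervention arm the implied variance is u₀ × u₁. At UC 50 that is an SD of √(50 × 39.7) ≈ 44.6, just within the limit there of √(39.7 × 50.3) ≈ 44.7. So at UC 50 the impossibility concerns the UC arm only. The 3-day optimism at UC 30 is reached only if every patient has either 0 or 90 uncovered days. These qualifications are correct. What remains is that the assumption is not stated.

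The protocol also promises revision: "Power estimates will be updated after Sites 2 and 3 are selected and preliminary data to inform analysis assumptions become available". Section 7.2 confirms the first condition, "Selection of Geisinger as Site 2 and Essentia as Site 3 occurred subsequent to the initial CCTN approval of the final protocol", but nothing shows that the preliminary data were available. A missed update is therefore not established.

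**Conclusion.** The Table 4 row for 30 × 50, ICC 0.03 is wrong by the table's own method, and so is the sentence drawn from it. The RR should be 0.793 and the detectable difference at UC 50 should be 10.3 days, so the text overstates it by 2.7 days (13.0 − 10.3). The stated fall to 37.0 days has about 95% power, not 80%. A digit transposition is the likely cause, but the conclusion does not depend on it. The exact corrected value rests on λ = 1, inferred from the agreement of the other 17 cells; the ordering error rests on no variance assumption.

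The unstated variance is a reporting gap whose effect differs by column. At this N_eff it is negligible at UC 50. At UC 70 the table asks for at least 5.4 days more than any feasible variance requires (60.9 − 55.5). At UC 30 it may be too optimistic by up to about 3 days (23.8 − 20.8). Neither part shows that H2.2 is underpowered.

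**What to change.** Replace the row with RR 0.793 and 23.8, 39.7 and 55.5 days. Reword the sentence so that OUD-CDS patients have at most 39.7 uncovered (at least 50.3 covered) days.

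Then recompute Table 4 with a stated UC mean and a stated patient-level SD that is feasible on the 0–90 day scale, taken from preliminary site data where available and otherwise shown as a range. Those results would supersede the corrected row; until then, state that the present figures assume a baseline mean of 1, if the authors confirm it. Two UC 50 entries in the 10 × 50 block (33.4 and 36.4) differ by 0.1 day from the computed 33.3 and 36.5 and can be checked in the same pass.

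The cost is one table row, one sentence and one recalculation, which fits the power update the protocol already foresees. The design, sample size and analysis do not change.

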13.3 Statistical Methods for Primary and Secondary Outcomes

This section provides an overview of the statistical methods to be employed in testing the primary and secondary outcomes. A more detailed description of the analysis may be found in the Statistical Analysis Plan. The Statistical Analysis Plan will provide more clarity about the underlying assumptions and methodological decisions regarding primary outcome analyses, including the extent to which either supplement alters the treatment effect.

Hypotheses for Aims 1 and 2 predict that the OUD-CDS intervention will increase the likelihood that patients at high risk of OUD are diagnosed with OUD (H1.1); and that among those at high risk or diagnosed with OUD it will increase the likelihoods that a naloxone rescue kit is ordered (H1.2) and that MOUD is ordered or the patient is referred to a provider who can order MOUD (H2.1), and the number of days covered by an MOUD prescription (H2.2). The hypotheses from Aims 1 and 2 will be tested using generalized linear mixed models so that the likelihood or counts of outcomes may be accurately estimated among OUD-CDS relative to UC clinics, accounting for the clustering of patients within randomized clinics. Binary outcomes (H1.1, H1.2, H2.1) will be normalized using a logistic-Normal link function, while it is anticipated that the count outcome (H2.2) will be normalized using a Poisson-Normal link function. The model will estimate fixed effects of OUD-CDS, care system and other covariates on outcomes, and random intercepts for clinics and patients (H1.1, H1.2, H2.1) or for clinics (H2.2).

Hypotheses for Aim 3 predict fewer ED visits (H3.1) and inpatient stays (H3.2) during the observation period of patients receiving care in the OUD-CDS relative to UC clinics. The rate at which each of these outcomes occurs per patient-year will be compared across clinics using generalized estimating equations. Clinic-aggregated counts of ED visits and inpatient stays will be normalized using a Poisson-Normal link function, and the intercept offset by the log of patient-years within the clinic. The model will estimate fixed effects of OUD-CDS, care system and other covariates on the rate of each outcome per patient-year. Should it be feasible, we will also collect and count ED visits and inpatient stays that occurred in the year prior to each patient’s index visit so that treatment group differences in pre-post changes in event rates can be quantified (i.e., treatment by time interaction).

Hypotheses for Aim 4 predict lower healthcare costs and the identification and mitigation of barriers and identification of facilitators to OUD-CDS implementation and uptake. **Analysis of costs** for this aim will include delivery costs of the OUD-CDS and incremental medical care costs attributable to the intervention, defined from the health system perspective. Intervention costs may include resources used for implementation, maintenance, compensation, and PCP and staff training – which may be assessed by interviews/surveys with implementation site staff or study resource use documentation, as appropriate – but will exclude research, development, and measurement costs, using standard micro-cost accounting methods and nationally-representative pricing of inputs. Medical care costs will include all prescribed medications and clinical inpatient, emergency, outpatient, and skilled nursing facility services incurred in the pre- and post-index observation periods by participants in each study group, as indicated by insurance claims and clinical encounter data. The study sample for the cost analysis will be participants who have continuous insurance coverage during the study period, including pharmacy benefits. This sample

will be compared to patients without continuous insurance coverage to assess representativeness and comparative completeness of utilization measurement in comparison to all study participants.

Paid amounts for medical claims that are specific to medical groups and insurance plans may provide a biased view of costs between pre- and post-intervention periods. To address this, claims will be converted to dollar amounts using Total Care Relative Resource Values™ (TCRRVs), which are a nationally standardized set of measures that have been endorsed by the National Quality Forum[50] and are derived from Centers for Medicare and Medicaid Services (CMS) relative value units (RVUs). TCRRVs extend CMS RVU measures to include utilization categories, such as laboratory services and medications, which do not have CMS RVU weights.[51] Inpatient costs are calculated by applying TCRRVs to the diagnosis-related group classification and length of stay of the hospitalization.

Standard health econometric and specification testing methods will be used to assess the incremental differences in healthcare costs between study groups [1, 2, 39]. Specifically, healthcare care costs will be analyzed using a generalized hierarchical model with a time x study group interaction term that can account for clinic-level clustering and the correlation in each subjects' repeated measures of costs over time (i.e., pre-index and post-index). Demographics and baseline clinical status will be controlled for based on randomization imbalances and model fit criteria. The marginal effect of being assigned to an intervention clinic will provide an estimate of the incremental medical cost associated with the OUD-CDS intervention. To account for the non-normality in costs, the distribution family will be specified appropriately, such as by using the modified Park test,[2] and the goodness of fit for the specified link function will be tested, such as by using modified Hosmer and Lemeshow and Pregibon link tests.[53, 54] Confidence intervals will be estimated using heteroscedasticity-robust estimation methods.[55]

Mixed method data analysis for Aim 5 will occur rapidly as data are collected, so that new information can support decision making about revisions in the implementation plan and adaptations as the study proceeds. All data analysis and subsequent conclusions and decisions made during live implementation will be carefully documented.

After the implementation phase is complete at all sites, monitoring data, survey data, and qualitative data from all sites will be triangulated to draw conclusions about the barriers, facilitators, adaptations, and recommendations for future dissemination of the OUD-CDS tool.

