13.6 Exploratory Analysis

Treatment effectiveness may vary as a function of contextual as well as patient factors. In secondary analyses of the primary outcomes, care system indicators (Site 1, Site 2, Site 3), clinic (e.g., proportion of primary care patients eligible for OUD-CDS, proportion of clinic patients with government-sponsored insurance), and provider (e.g., waiver status, number of patients eligible for OUD-CDS, confidence in treating patients with OUD, intent to prescribe buprenorphine if waiver no longer required) characteristics may be added to the primary model as main effects and in interaction with the treatment group indicator to assess treatment heterogeneity due to contextual factors. Patient characteristics (e.g., race, ethnicity, age, estimated neighborhood income and education, documented heroin vs. oral opioid use) may be similarly added to assess treatment heterogeneity due to patient factors.

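### H2.2 (MOUD days covered): a Poisson model with only a clinic intercept makes tests of patient-level factors and treatment-by-patient-factor interactions severely anti-conservative, while the primary treatment test stays near nominal

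*Combined protocol and SAP*

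**What the plan says.** Section 13.1.2 lists H2.2 among the primary outcomes: "Total days covered by an MOUD prescription in the 90 days after index visit for patients with OUD or identified by the OUD-CDS" (diagnosed patients plus those whom the tool flags for elevated risk). Each patient contributes one total between 0 and 90.

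Section 13.3 plans generalized linear mixed models for Aims 1 and 2. For H2.2, "it is anticipated that the count outcome (H2.2) will be normalized using a Poisson-Normal link function". The random effects are "random intercepts for clinics and patients (H1.1, H1.2, H2.1) or for clinics (H2.2"), so the binary outcomes get a patient intercept and H2.2 does not. Section 13.4 says of the primary comparisons by treatment group: "These comparisons will be evaluated using a two-sided test with a Type I error rate of 5" percent.

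Patient-factor analyses of the primary outcomes appear in three places. Section 2.1 (Secondary Analyses) commits the study to assessing whether effectiveness varies with site, clinic, provider or patient characteristics. Section 5.2 says patient characteristics may be added to the primary model. Section 13.6 repeats this: characteristics such as race, ethnicity, age, neighborhood income and education, and heroin versus oral opioid use "may be similarly added to assess treatment heterogeneity due to patient factors".

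Sections 13.3 to 13.7 give H2.2 no dispersion parameter, negative binomial, two-part or bounded-count model, and no robust standard error. Robust intervals and tests of the distribution family are specified only for Aim 4 costs.

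**The concern.** A Poisson model sets the variance within a clinic equal to the mean. Prescription coverage does not behave like that: many patients may have none, and those treated tend to have long blocks of days. The plan recognizes the 0-90 bound when computing power, where it models uncovered days "to ensure that the estimated days in both groups remained between 0 and 90 days", but the analysis model has neither the bound nor room for extra patient-level variance.

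The effect depends on where a term varies. Treatment, care system and clinic characteristics vary only between clinics, and the estimated clinic variance takes up the excess. Patient characteristics vary within clinics, where the model allows only Poisson noise. Their standard errors are then too small by about the square root of the variance-to-mean ratio. At stake are subgroup statements on a primary outcome, for example by race or age, that could be noise and could still influence whom such tools are aimed at.

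**Working it through.** **Inputs.** From Section 13.2.2.1: "conservative assumptions regarding the numbers of randomized clinics (10, 30, 50) and of eligible patients (50 or 100 per clinic"), ICC values 0.01, 0.03 and 0.05 described as "a range of clinic intraclass correlations consistent with those observed for other process measures at HealthPartners", and usual-care means of 70, 50 or 30 uncovered days, that is 20, 40 or 60 covered. Two-sided 5% is from Section 13.4. The shape of the distribution and the share of zeros are not stated, so several shapes are assumed.

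**The plan's own figures.** The documents give no error rate for patient-factor tests. The only H2.2 figures are in Table 4. With N_eff = clinics × m / (1 + (m − 1) × ICC) and the standard Poisson-regression power formula at a base rate of 1 per patient, 17 of the 18 rate ratios reproduce to three decimals. The exception is the cell used in the worked example (30 clinics, 50 patients, ICC 0.03). There N_eff = 1500 / 2.47 = 607.3, which gives 0.793 (39.7 days at a mean of 50) against the stated 0.739 (37.0 days). The stated value also lies below the 0.760 given for ICC 0.05, which is out of order. It looks like transposed digits and is a separate correction.

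**Closed form for a patient-level term.** Let φ = variance/mean of days covered within clinic. A model-based Wald test then has

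type I error = 2 × (1 − Φ(1.96 / √φ)).

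With mean μ covered days:

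| Assumed distribution | φ | μ = 20 | μ = 40 | μ = 60 |
|---|---|---|---|---|
| 0 or 90 days | 90 − μ | φ 70: 82% | φ 50: 78% | φ 30: 72% |
| Zeros plus uniform 1-90 | 181/3 − μ | φ 40.3: 76% | φ 20.3: 66% | not attainable (maximum 45.5) |
| Beta-binomial, a + b = 4, no extra zeros | (94/5) × (1 − μ/90) | φ 14.6: 61% | φ 10.4: 54% | φ 6.3: 43% |

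Example: φ = 50 gives 1.96/7.07 = 0.277, and 2 × (1 − Φ(0.277)) = 0.78. Standard errors are too small by √φ, from √6.3 = 2.5 to √70 = 8.4 times. The formula contains neither the number of clinics nor the number of patients, so a larger sample does not help. Reaching 80% needs φ of about 60.

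**Zero-heavy case.** As a rough proxy for the share with any coverage, take the 2-20% usual-care rates used to power the binary outcomes, including 30-day MOUD order or referral. With days uniform on 1-90, φ = 60.3 − 45.5 × share, or 59.4 at 2% and 51.2 at 20%. Type I error is then 80% to 78%. Existing supply or orders after day 30 would raise the share covered.

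**Simulation under the null.** Poisson mixed model, clinic intercept only, model-based Wald tests, 30 clinics × 50 patients, 3 care systems, about 600 replicates per row. Rejection rates in percent:

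| Data | Treatment | Patient factor | Treatment × patient factor | Treatment × clinic factor | Treatment × care system |
|---|---|---|---|---|---|
| 10% with any coverage, uniform 1-90 | 7.2 | 79.6 | 80.5 | 10.5 | 7.5 |
| 0 or 90, mean 40 | 6.2 | 75.0 | 78.3 | 7.5 | 9.3 |
| Beta-binomial, mean 40 | 9.8 | 55.9 | 52.4 | 8.8 | 10.4 |

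Monte Carlo error is about √(0.8 × 0.2 / 600) = 1.6 points near 80%. Part of the excess over 5% in the between-clinic columns comes from using a normal reference with 30 clinics. Provider-level factors were not simulated.

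**Does the remedy work?** In 4,000 null data sets (30 × 50), the patient-factor test with a clinic-clustered sandwich standard error and t on 29 degrees of freedom rejected 4.8% (10% covered, uniform) and 4.9% (0 or 90, mean 40). The model-based Poisson standard error rejected 79% and 77% in the same data. For the interaction, a Poisson model with clinic fixed effects (10% covered, uniform) rejected 77% with model-based standard errors, against 4% with either a quasi-Poisson scale or clinic-clustered standard errors.

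**The case against.** The strongest reply is that little of consequence is touched. Section 13.4 attaches its 5% error rate for H2.2 to the comparison by treatment group, and that test is near nominal. The affected tests sit mainly under exploratory analysis, are worded as optional in Sections 5.2 and 13.6, and carry no confirmatory claim. The Poisson model is only anticipated. Section 13.1.5 asks for links suited to the distribution, and Section 13.3 calls itself an overview and defers methodological decisions to a Statistical Analysis Plan. These points limit the weight of the finding. They do not answer it: Section 2.1 says the study will assess variation by patient characteristics, and no safeguard for H2.2 appears in the text available.

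Two stronger readings are tempting, and the documents do not support them. A reader might infer that the primary H2.2 test, or all planned heterogeneity tests, fail at about 80%. Care-system and clinic-factor interactions are tested between clinics and reject at about 7-11%. Provider factors vary within clinics and cannot be assumed safe, but there is no figure for them. A reader might also take 80% as a property of the trial. It needs a zero-heavy distribution that the documents do not give. The 10%-covered scenario has a mean of only 0.10 × 45.5 = 4.55 days, well under the plan's 20-60.

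**Conclusion.** The point holds for patient-level factors and treatment-by-patient-factor interactions in the H2.2 model. At the plan's means of 20-60 covered days, the type I error of a model-based test of a patient-level term is about 43-82% under the shapes tried, and 43-61% when no extra mass at zero is assumed. It is near 80% if most patients have no covered days. Even the lowest figure is more than eight times nominal (43/5 = 8.6); a distribution less dispersed than those tried would give less. The primary treatment comparison is at most mildly inflated (about 6-10%), as are care-system and clinic-factor interactions (about 7-11%). The conclusion assumes that the model is fitted as Section 13.3 describes, with model-based standard errors, and that the patient factor varies within clinics. It is worth settling before analysis, but it does not threaten the main H2.2 result.

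**What to change.** State in the SAP, for H2.2 and for the Section 13.6 patient-factor analyses of H2.2, one of the following, keeping the clinic random effect:

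- clinic-clustered robust standard errors with a small-sample correction, replacing the Poisson model-based ones; or
- an overdispersed model of days covered out of 90 (beta-binomial or quasi-binomial), or a two-part model separating any coverage from the number of days.

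Use the same choice for the main model and the interactions, and report the share of patients with zero days. The cost is SAP wording, a little more analysis work in standard software, and wider, more honest intervals for patient-level terms. The main treatment test is little changed.
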